14.4. ECG**14.4.1. Available Data**

The following provided ECG parameters will be analyzed: heart rate, RR interval, PR interval, QRS interval, uncorrected QT interval, QT interval corrected for the heart rate using Fridericia's formula (QTcF) and QT interval corrected for the heart rate using Bazett's formula (QTcB).

14.4.2. Number of Significant Digits

The standardized results of continuous ECG parameters will be mapped to analysis values without rounding.

Only for printing in the analysis TLFs, a maximum of 3 decimal positions will be shown.

14.4.3. Derivation of ECG Parameters

No derivation of ECG parameters will be done. Data as recorded in the CRF/external ECG vendor file will be used for analyses.

14.4.4. Handling of ECGs Measured in Triplicate

The mean over the triplet will be calculated for each parameter. Mean values will be derived during the statistical analysis. Only means will be reported in tables and listings.

14.4.5. Definition of Normal Ranges and Abnormalities

For the QT, QTcF and QTcB parameters, the following categorizations will be done:

- of the actual values:
 - ≤ 450 ms (considered as normal range),
 -]450,480] ms,
 -]480,500] ms,
 - >500 ms;
- of the changes from baseline:
 - ≤ 30 ms (including all decreases in QT) (considered as normal range),
 -]30,60] ms,
 - >60 ms.

For PR, the following categorizations will be done:

- < 120 ms,
- [120, 220] ms (considered as normal range),
- >220 ms;

For heart rate, the following categorizations will be done:

- < 50 bpm,
- [50, 100] bpm (considered as normal range),
- >100 bpm;

14.4.6. Definition of Treatment-emergent ECG Abnormalities

Actual value: An abnormal post-baseline abnormality is defined as treatment-emergent when the abnormality is worse compared to the abnormality at baseline. When the baseline value is missing, post-baseline abnormalities are always considered as treatment-emergent.

An abnormal category for change from baseline is always treatment-emergent.

14.4.1. Determination of Worst-case Abnormality

The worst-case post-baseline categorized actual analysis value and the worst-case categorized change from baseline will be determined per subject and per parameter, using all non-missing post-baseline records (including unscheduled and follow-up visits).

The worst-case categorized actual analysis value is the category corresponding to the highest post-baseline actual value.

The worst-case change from baseline is the category corresponding to the largest increase (positive change) from baseline.

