14.4.2. Tables

Table 14.3.3.1: ECG: Descriptive statistics of the actual values and change from baseline per time point

Descriptive statistics of the actual values and changes from baseline (including 95% CI of the mean for change from baseline values) per parameter, treatment group and analysis visit/time point.

Population: safety analysis set.

Table 14.3.3.2: ECG: Worst-case shift table of the categorized actual values

This table will present the shift in categorized actual values for the worst-case versus the categorized baseline value per parameter (QT, QTcF, QTcB, PR and HR) and treatment group.

Population: safety analysis set.

Table 14.3.3.3: ECG: Worst-case treatment-emergent categorized QT and QTc actual value abnormalities

Frequency table of the treatment-emergent categorized abnormal actual values per parameter (QT, QTcF and QTcB), treatment group for the worst-case.

Population: safety analysis set.

Table 14.3.3.4: ECG: Worst case treatment-emergent HR and PR actual values abnormalities

Frequency table of the treatment-emergent categorized (L, N, H) abnormal actual values per parameter (PR and HR), treatment group for the worst-case.

Population: safety analysis set.

Table 14.3.3.5: ECG: Worst-case treatment-emergent categorized abnormal changes from baseline in QT and QTc

Frequency table of the worst-case treatment-emergent categorized abnormal changes from baseline per parameter (QT, QTcF and QTcB) and treatment group.

Population: safety analysis set.

Table 14.3.3.6: ECG: Frequency table of the eCRF ECG interpretation per time point

Frequency table per treatment group and time point of the ECG interpretation scores. Interpretation scores are: Normal/Abnormal.

Population: safety analysis set.

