14.4.3. Listings

Next to the actual values and the changes from baseline, all listings will present the following parameters:

- The abnormality of the actual values and of changes from baseline;
- Any input related interpretations of the ECG;
- Any related comments.

Listing 16.2.12.1: ECG: Full listing

Listing per treatment group, per subject, parameter and analysis visit/time point of all data.

Population: safety analysis set.

Listing 16.2.12.2: ECG: Listing of treatment-emergent abnormalities

Listing per treatment, subject, parameter and analysis visit/time point showing only analysis visits/time points having treatment-emergent abnormal results (on actual value and/or on changes from baseline). Next to the selected analysis visits/time points, the baseline record will fully be presented at all times.

Population: safety analysis set.

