14.5.4. Definition of Normal Ranges and of Abnormalities

The actual analysis values for the following vital signs parameters will be categorized into abnormality classes according to their position to normal range (table below), defining these classes as low (L), normal (N) or high (H).

Values within or equal to the normal range boundaries are considered normal (N). Values below the lower limit of the normal range are categorized as low (L), and values above the upper limit of normal range are categorized as high (H).

| Parameter (unit) | Normal range | |
|------------------|--------------|-------------|
| | Lower limit | Upper limit |
| Heart rate (bpm) | 40 | 100 |
| DBP (mmHg) | 45 | 90 |
| SBP (mmHg) | 90 | 140 |
| Temperature (°C) | 35.5 | 37.5 |

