14.5.5. Definition of Treatment-emergent Vital Signs Abnormalities

A post-baseline abnormality class L or H is defined as treatment-emergent when it differs from the abnormality class at baseline. If the baseline result is missing, a post-baseline abnormality L or H will always be considered as treatment-emergent.

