14.5.6. Determination of the Worst-case Abnormality

The following worst-case post-baseline abnormalities L, N or H will be determined per subject and per parameter, using all non-missing post-baseline records (including unscheduled and follow-up visits):

- H = high:
At least one post-baseline result is classified as H, and there are no results classified as L.
- L = low:
At least one post-baseline result is classified as L, and there are no results classified as H.
- H+L = high and low:
At least one post-baseline result is classified as H, and at least another post-baseline result is classified as L.
- N = normal: All post-baseline results are classified as N.

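### The ECG worst-case rule takes the highest value for every parameter, so Tables 14.3.3.2 and 14.3.3.4 under-count subjects with low heart rate or short PR

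*SAP*

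**What the plan says.** SAP section 14.4 numbers its subsections 14.4.1 to 14.4.3 twice. The second 14.4.1 defines the worst case separately for each subject and parameter, over all available post-baseline ECGs, unscheduled and follow-up ones included. For actual values it reads: "The worst-case categorized actual analysis value is the category corresponding to the highest post-baseline actual value". No parameter is excepted.

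Section 14.4.5 sets the categories. QT, QTcF and QTcB are one-sided: 450 ms or less is normal and the other classes are higher. PR and heart rate are two-sided. After "For heart rate, the following categorizations will be done" come classes below 50, 50 to 100 (normal) and above 100 bpm; PR has below 120, 120 to 220 (normal) and above 220 ms.

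In the second 14.4.2, the worst-case shift table (14.3.3.2) covers PR and heart rate as well as the QT parameters. Table 14.3.3.4 is described as: "Frequency table of the treatment-emergent categorized (L, N, H) abnormal actual values per parameter (PR and HR), treatment group for the worst-case".

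Section 14.4.6 adds: "An abnormal post-baseline abnormality is defined as treatment-emergent when the abnormality is worse compared to the abnormality at baseline".

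**The concern.** A highest-value rule finds the worst case only when abnormality lies in one direction. For PR and heart rate, one normal reading removes any number of low ones. The treatment-emergent definition compounds this: worse than baseline has no meaning for a move between low and high, because the SAP does not order those two classes.

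Safety is the primary objective, and the SAP chose to tabulate low heart rate and short PR by arm. A low cell at or near zero would be read as showing that such subjects were absent, when the rule itself can produce the zero.

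**Working it through.** **1. What follows from the text alone.** For a subject with post-baseline values y1, …, yk and lower limit c (50 bpm or 120 ms):

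- rule as written: low if max(y) < c, that is, if every value is below c;
- two-directional rule: low if min(y) < c, that is, if any value is below c.

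The first condition implies the second, so the tabulated low count can never exceed the number of subjects with a low value. The two are equal only if every such subject is low at every post-baseline ECG.

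Examples: 42 and 80 bpm give a maximum of 80, hence normal. The series 48, 47, 62, 46, 49, 47, 48 bpm gives a maximum of 62, hence normal, although six of seven readings are below 50.

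**2. Comparison within the SAP.** The vital-signs section (14.5.6) assigns low when "At least one post-baseline result is classified as L, and there are no results classified as H", and has a separate class for subjects with both; the laboratory section (14.3.8.1) does the same. Section 14.5.5 avoids ordering the classes: "A post-baseline abnormality class L or H is defined as treatment-emergent when it differs from the abnormality class at baseline". Section 8.2.1 explains that the ECG normal ranges were changed for consistency with other studies, but gives no reason for a one-directional worst case.

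**3. Number of ECGs.** SAP 5.2 gives seven scheduled post-baseline time points: Day 1 at 1 h, Day 43 pre-dose, Day 43 at 1 h, and Days 57, 85, 113 and 169.

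**4. Illustration of size.** The documents give no mean or SD for heart rate or PR, so these are assumptions. Model: value = subject mean + independent within-subject error, both normal; baseline is the mean of a triplicate; no drug effect; 400,000 simulated subjects per scenario.

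- Heart rate: mean 62–68 bpm, between-subject SD 8–10, within-subject SD 5–6 (27 scenarios).
- PR: mean 150–155 ms, between-subject SD 18–20, within-subject SD 8 (9 scenarios).

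| Seven ECGs | Heart rate < 50 bpm | PR < 120 ms |
|---|---|---|
| Any low value | 9.6–35.7% (4–14 of 40) | 9.8–17.7% (4–7 of 40) |
| Labelled low by the rule | 0.15–3.7% (0.1–1.5 of 40) | 0.7–2.3% (0.3–0.9 of 40) |
| Missed, within scenario | 88–99% | 87–93% |
| Treatment-emergent, any low | 7–25% | 7–11% |
| Treatment-emergent, kept by the rule | 0.01–0.30% | 0.03–0.17% |
| Treatment-emergent, missed | at least 98% | at least 98% |

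The treatment-emergent ranges cover triplicate baseline errors that are independent or fully correlated.

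**5. The plan's own detection yardstick.** Protocol 7.1 states an 87% chance of seeing at least one case of an event with 5% incidence in 40 subjects: 1 − 0.95^40 = 0.8715, which reproduces. It concerns adverse events, but the same formula shows the effect here. With heart rate mean 65, SDs 8 and 6, the treatment-emergent low proportion is 17.6% by the any-low rule and 0.033% by the rule as written. The chance of at least one such subject in 40 is 1 − (1 − 0.176)^40 > 0.999 and 1 − (1 − 0.00033)^40 = 0.013.

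**6. Sensitivity.**

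- Three ECGs per subject (corner scenarios): 71–93% of all lows and 90–97% of treatment-emergent lows are missed. With one ECG the two rules agree.
- Other assumed distributions (heart rate mean 60–70, PR mean 150–160): any low 17–41% against 0.3–2.4% labelled low for heart rate; 12–14% against 1.0–3.1% for PR.
- Hypothetical 5 bpm fall on MOR106: the arm difference in treatment-emergent low heart rate is 13–22 percentage points by the any-low rule and 0.3–1.6 points by the rule as written.
- Larger hypothetical falls, seven ECGs, treatment-emergent lows per 40 subjects: 10 bpm gives 23.7 (any low) against 1.6 (rule); 20 ms in PR gives 15.0 against 2.5.

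**The case against.** The strongest reply is that little would be hidden in practice.

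- **Mean change.** Table 14.3.3.1 gives mean change from baseline with a 95% CI at each time point. With the SDs assumed above, the SD of change runs from 5 × √(1 + 1/3) = 5.8 to 6 × √2 = 8.5 bpm. With 40 subjects the half-width is 2.02 × SD / √40, or about 1.8 to 2.7 bpm. A uniform 5 bpm fall would be visible there, and vital-signs heart rate is summarised in the same way at 12 post-baseline visits.
- **Individual values.** Every low value is in Listing 16.2.12.1. Listing 16.2.12.2 shows time points "having treatment-emergent abnormal results (on actual value and/or on changes from baseline").
- **Adverse events.** Clinically significant ECG findings are recorded as AEs (protocol 6.5.5) and counted by arm.
- **Importance.** The primary endpoints are TEAEs, SAEs and AESIs, the safety analysis is descriptive, and development in atopic dermatitis had already stopped for futility.
- **Size.** The percentages rest on assumed distributions.

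All of this stands as a limit on impact. It does not rescue the two tables. A mean change or a minimum is not a count of subjects, and a fall confined to a few subjects moves the mean little. Vital signs do not fill the gap: their limits are "Heart rate (bpm) | 40 | 100", so 40–49 bpm is normal there, and PR is not a vital sign. Table 14.3.3.6 gives only normal or abnormal for the ECG as a whole. Low values that the investigator does not judge clinically significant are therefore counted by arm nowhere else.

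**Conclusion.** The concern holds. That the post-baseline low counts for PR and heart rate cannot be too large, and are too small whenever a subject has both low and non-low readings, follows from the wording without any assumption.

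That the treatment-emergent low cells of Table 14.3.3.4 are almost empty depends on the assumed distributions. It holds over the no-effect ranges examined with seven ECGs, and largely with three (at most about 0.16 expected subjects per 40 in the scenarios counted that way). It weakens with a large sustained fall or very few ECGs.

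The error is confined to the worst-case low column of Table 14.3.3.2 and the low cells of Table 14.3.3.4, with a matching excess elsewhere, mainly in the normal class. The baseline rows, the high counts and all QT and QTc results are correct. The missing order between low and high in 14.4.6 is a smaller defect, affecting only subjects who move from one abnormal side to the other. This should be fixed, but it does not threaten the primary endpoint.

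**What to change.** - **Second 14.4.1:** limit the highest-value rule to QT, QTcF and QTcB. For PR and heart rate, apply the L / H / H+L / N classification of 14.3.8.1 and 14.5.6 to all post-baseline ECGs.
- **14.4.6:** for PR and heart rate, call a post-baseline low or high class treatment-emergent when it differs from the baseline class, as in 14.5.5.
- **Tables 14.3.3.2 and 14.3.3.4:** add the H+L class for these two parameters.

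This takes two or three sentences, reuses the vital-signs logic and needs no new data. If the database is already locked, record the change and its reason in the CSR, as SAP 8.2.2 provides.

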14.4.2. Tables

Table 14.3.3.1: ECG: Descriptive statistics of the actual values and change from baseline per time point

Descriptive statistics of the actual values and changes from baseline (including 95% CI of the mean for change from baseline values) per parameter, treatment group and analysis visit/time point.

Population: safety analysis set.

Table 14.3.3.2: ECG: Worst-case shift table of the categorized actual values

This table will present the shift in categorized actual values for the worst-case versus the categorized baseline value per parameter (QT, QTcF, QTcB, PR and HR) and treatment group.

Population: safety analysis set.

Table 14.3.3.3: ECG: Worst-case treatment-emergent categorized QT and QTc actual value abnormalities

Frequency table of the treatment-emergent categorized abnormal actual values per parameter (QT, QTcF and QTcB), treatment group for the worst-case.

Population: safety analysis set.

Table 14.3.3.4: ECG: Worst case treatment-emergent HR and PR actual values abnormalities

Frequency table of the treatment-emergent categorized (L, N, H) abnormal actual values per parameter (PR and HR), treatment group for the worst-case.

Population: safety analysis set.

Table 14.3.3.5: ECG: Worst-case treatment-emergent categorized abnormal changes from baseline in QT and QTc

Frequency table of the worst-case treatment-emergent categorized abnormal changes from baseline per parameter (QT, QTcF and QTcB) and treatment group.

Population: safety analysis set.

Table 14.3.3.6: ECG: Frequency table of the eCRF ECG interpretation per time point

Frequency table per treatment group and time point of the ECG interpretation scores. Interpretation scores are: Normal/Abnormal.

Population: safety analysis set.

14.4.3. Listings

Next to the actual values and the changes from baseline, all listings will present the following parameters:

- The abnormality of the actual values and of changes from baseline;
- Any input related interpretations of the ECG;
- Any related comments.

Listing 16.2.12.1: ECG: Full listing

Listing per treatment group, per subject, parameter and analysis visit/time point of all data.

Population: safety analysis set.

Listing 16.2.12.2: ECG: Listing of treatment-emergent abnormalities

Listing per treatment, subject, parameter and analysis visit/time point showing only analysis visits/time points having treatment-emergent abnormal results (on actual value and/or on changes from baseline). Next to the selected analysis visits/time points, the baseline record will fully be presented at all times.

Population: safety analysis set.

14.5. VITAL SIGNS

14.5.1. Available Data

The following provided vital signs parameters will be analyzed: weight, heart rate, diastolic and systolic blood pressure and temperature.

14.5.2. Number of Significant Digits

The standardized results of continuous vital signs parameters will be mapped to analysis values without rounding.

Only for printing in the analysis TLFs, a maximum of 3 decimal positions will be shown.

14.5.3. Derivation of Vital Signs Parameters

NAP.

14.5.4. Definition of Normal Ranges and of Abnormalities

The actual analysis values for the following vital signs parameters will be categorized into abnormality classes according to their position to normal range (table below), defining these classes as low (L), normal (N) or high (H).

Values within or equal to the normal range boundaries are considered normal (N). Values below the lower limit of the normal range are categorized as low (L), and values above the upper limit of normal range are categorized as high (H).

| Parameter (unit) | Normal range | |
|------------------|--------------|-------------|
| | Lower limit | Upper limit |
| Heart rate (bpm) | 40 | 100 |
| DBP (mmHg) | 45 | 90 |
| SBP (mmHg) | 90 | 140 |
| Temperature (°C) | 35.5 | 37.5 |

14.5.5. Definition of Treatment-emergent Vital Signs Abnormalities

A post-baseline abnormality class L or H is defined as treatment-emergent when it differs from the abnormality class at baseline. If the baseline result is missing, a post-baseline abnormality L or H will always be considered as treatment-emergent.

14.5.6. Determination of the Worst-case Abnormality

The following worst-case post-baseline abnormalities L, N or H will be determined per subject and per parameter, using all non-missing post-baseline records (including unscheduled and follow-up visits):

- H = high:
At least one post-baseline result is classified as H, and there are no results classified as L.
- L = low:
At least one post-baseline result is classified as L, and there are no results classified as H.
- H+L = high and low:
At least one post-baseline result is classified as H, and at least another post-baseline result is classified as L.
- N = normal: All post-baseline results are classified as N.

14.5.7. Tables

Table 14.3.4.1: Vital signs: Descriptive statistics of the actual values and change from baseline per time point

Descriptive statistics of the actual values and changes from baseline (including 95% CI of the mean for change from baseline values) per parameter, treatment group and analysis visit/time point.

Table 14.3.4.2: Vital signs: Worst-case shift table according to the normal range

This table will present the shift in abnormality (L/N/H) for the worst-case versus the baseline abnormality (L/N/H) per parameter and treatment group. Parameters without normal ranges will not be presented.

Population: safety analysis set.

Table 14.3.4.3: Vital signs: Worst-case treatment-emergent abnormalities

Frequency table of the treatment-emergent abnormalities per parameter, treatment group for the worst-case. Parameters without normal ranges will not be presented.

Population: safety analysis set.

14.5.8. Listings

Next to the actual values and the changes from baseline, all listings will present the following parameters:

- The value abnormality (result position versus normal range, L or H);
- The normal range associated to the parameter value;
- Position in which the measurement was taken (sitting, standing or supine).

Listing 16.2.13.1: Vital signs: Full listing

Listing per treatment group, per subject, parameter and analysis visit/time point of all data.

Population: safety analysis set.

Listing 16.2.13.2: Vital signs: Listing of treatment-emergent abnormalities

Listing per treatment, subject, parameter and analysis visit/time point showing only analysis visits/time points having treatment-emergent results. Next to the selected analysis visits/time points, the baseline record will fully be presented at all times.

Population: safety analysis set.

14.6. PHYSICAL EXAMINATIONS

Listing 16.2.14.1: Physical examinations: Abnormalities

Listing per treatment group, per subject and per analysis visit/time point only showing the visits having abnormal physical examination findings.

Population: safety analysis set.

16. APPENDIX

16.1. PK DATA REVIEW

For the review of PK/ data, following items should be checked:

- I. PK
 - I.1. MISSING PK DATA
 - I.1.1. Missing concentrations/measurement
 - I.2. REVIEW OF PK PROFILES AND CONCENTRATION VALUES
 - I.2.1. Abnormal PK concentration/measurement profiles
 - I.2.2. Abnormal PK concentration/measurement data point
- II. PK ANALYSIS SET
- II. PK ANALYSIS SET
